The use of immersive virtual reality during robot-assisted walking in healthy adults: a study protocol

Effect of changing the optic flow speed in two different virtual environments on active participation during robot-assisted walking.

Synopsis

The aim of this study will be to investigate the effect of changing the optic flow speed on active participation during robot-assisted walking with the Lokomat-system in healthy adults. Second, the aim is to investigate the effect of two different virtual environments on active participation. The Lokomat is a gait exoskeleton that comprises two actuated leg orthoses and is used in conjunction with a body-weight support and treadmill. 28 participants, divided equally into 2 groups, will be tested in the rehabilitation center TrainM (Antwerp). Participants will perform one virtual-reality (VR) enhanced robot-assisted gait training (RAGT) session under three conditions for 7 minutes each: 1) walking with slower optic flow speed, 2) walking with matched optic flow speed, and 3) walking with fast optic flow speed. The virtual environment will be different for both groups: the experimental group will walk in a more interactive virtual environment such as a park or city street whereas the control group will walk in a virtual environment representing an endless hallway. Active participation will be assessed with the use of electromyography (EMG) and the position and force sensors of the Lokomat.

Key words: Robot-Assisted Gait Training, Lokomat, Virtual Reality, Optic Flow, Stroke

[name]. [name], Brussel 7/12/2017

1. Introduction

1.1 Rationale

The recovery of functional gait is of great importance for neurological patients and is a common goal of their rehabilitation programs [1]. Treadmill training with or without body weight support (BWS) is often used in clinics as a therapeutic approach for improving patients' gait function [2]. A more recent strategy to enhance gait training is robot-assisted gait training (RAGT), combining robotics with BWS treadmill training [1]. Both treadmill training and RAGT have demonstrated improvements in regaining the ability to walk in different neurological populations [3-6]. However, an important problem of using a treadmill for gait training is the incorrect visual information subjects receive during treadmill walking [2].

Controlling our locomotion involves the integration of visual, vestibular and proprioceptive information [7]. An important source of visual information to guide locomotion is optic flow (OF), a pattern of visual motion projected onto the retina of the eye [2, 8]. Optic flow, induced by locomotion, provides us with information about the direction and speed of self-motion [2, 7-9]. However, during treadmill walking, the visual information about the direction and speed of walking is inconsistent with the proprioceptive input of the lower limbs [2]. Subjects are walking on the treadmill and yet, their environment remains static.

It has already been shown that manipulating the OF can induce changes in humans' locomotion. Studies in healthy volunteers and neurological patients have shown that walking speed can be altered by changing the OF speed while walking on a treadmill [7, 9-13]. A negative correlation between walking speed and OF speed has been found, indicating that subjects will walk faster at a slower optic flow speed and vice versa. By manipulating the OF speed, a mismatch will arise between the OF and the proprioceptive information of the lower extremities and gait parameters will be adjusted [2, 7].

This manipulation of the OF can be done with the use of virtual reality (VR) where patients walk in a virtual environment (VE). VR devices and systems can be classified into two categories: (1) Semi-immersive or non-immersive VR systems, who let the user perceive both real world and a part of the VE (e.g. TV-screens, projection screens), and (2) Immersive VR systems, who fully integrate the user into the VE, by blocking out perception of the real world (e.g. head-mounted displays (HMD)) [14].

Although various studies have already investigated the effects of manipulating the OF on gait parameters, all these studies used either overground training or treadmill training to obtain locomotion. None of these studies assessed the effect of OF speed alterations during RAGT. Even more, the majority of these studies used non-immersive VR systems while this study will provide subjects with an immersive VE with the use of a HMD. Since this will be the first study investigating the effect of manipulating the OF during RAGT by means of an exoskeleton, a healthy population will first be tested before performing this on neurological patients. Furthermore, this study is also going to investigate if the type of VE has an influence on the active participation.

1.2 Objective

The aim of this study is to investigate the effect of different OF speeds on active participation in healthy participants during VR-enhanced RAGT by means of an exoskeleton.

The second aim is to investigate the effect of two different VEs on active participation during RAGT.

2. Methods

2.1 Study design

An experimental, 2-group, single-center trial will be conducted in which healthy participants will perform one VR-enhanced RAGT session in which 3 different optic flow (OF) speeds will be presented in a random order: 1) walking with slow OF speed, 2) walking with matched OF speed, and 3) walking with fast OF speed. The VE will be different for both groups. The experimental group will walk in a more interactive VE, whereas the VE of the control group will be a more static environment.

2.2 Participants

2.2.1 Number

Based on a sample size calculation (G*Power 3.0.10) (F-tests, repeated measures ANOVA, within-between subjects) with Cohen's f of 0.25 (moderate effect size), type 1 error probability of 0.05, power of 0.80 for 2 groups and 3 conditions, a total of 28 participants, divided equally in 2 groups, need to be recruited. In case subjects drop out, additional participants will be tested till 14 participants in each group completed all conditions. Participants will be tested in the rehabilitation center TrainM in Antwerp.

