2.4 Procedure

Participants will be tested during one VR enhanced RAGT session at the rehabilitation center TrainM (Antwerp).

Prior to the start of the experiment, surface electrodes will be placed bilateral on the Mm. rectus femoris and Mm. biceps femoris to measure muscle activity. Electrode placement will follow as closely as possible the guidelines of SENIAM [16]. The skin underlying the electrode will be shaved and cleaned to improve electrode–skin contact and reduce impedance.

At the start of the session, participants will be habituated to walking in the Lokomat without the virtual reality. During this habituation trial, the appropriate settings to walk comfortable in the exoskeleton will be determined. To make sure all participants walk comfortable in the Lokomat, subjects will be provided with a body weight support (BWS) of 30%. Guidance force (GF) will be set on 80% for all participants. With lower levels of GF, the biofeedback values will show smaller changes and can become negligible. Lastly, the walking speed (WS) will be set at 2.8 km/h for all participants (setting Lokomat: see Appendix). Preparing and installing the participant and determining the appropriate Lokomat settings will take no longer than 20 minutes. When the Lokomat settings are defined, the Lokomat will be stopped for a moment so that the virtual reality can be added. Participants will put on the HMD and will start walking again for one minute while watching the virtual environment scene expanding at a speed matching their walking speed to get used to the VR. After the habituation trial, participants will walk in the Lokomat with the three different OF speeds [10, 15] that will be presented in a random order for 7 minutes each:

- 1) slower OF: 0.5 times the individual's comfortable speed,
- 2) matched OF: same as the individual's comfortable speed,
- 3) faster OF: 2 times the individual's comfortable speed.

In order to normalize the registered EMG signals, the maximum voluntary isometric contraction (MVIC) test will be used. Each subject carries out the MVIC test 3 times for each muscle. Subjects must reach their maximum strength as quickly as possible and must keep it for 6 seconds. Subjects will perform the MVIC test in the following testing positions: prone with the knees in 30° of flexion (Mm. biceps femoris); seated with the knees in 60° of flexion, and the hips in 90° of flexion (Mm. rectus femoris). The average of the three tests will be taken for each muscle.

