2.7 Outcome

2.7.1 Biomechanical quantification of active participation

The active participation during RAGT will be measured with the use of electromyography, the force sensors and the position sensors of the Lokomat.

- **Electromyography:** with the use of surface electrodes, muscle activity of the Mm. rectus femoris and Mm. biceps femoris of both legs will be measured. Surface electromyograms of these muscles will be analyzed with the use of the 'mean absolute value' variable. It represents the area under the EMG signal (AUC) once it has been rectified, meaning that all of the negative voltage values have been made positive. The mean absolute value will be measured per minute to compare the amount of muscle activity in time within one OF speed, between different OF speeds and between the 2 VEs.

- **Force sensors:** with the use of the force sensors of the Lokomat, interaction torques between the participant and the orthosis will be measured of the 4 joints (bilateral hip and knee). These interaction torques will be used to quantify how much the participant contributes to the walking movement him or herself. The average of these interaction torques will be calculated per minute to compare the amount of force in time within one OF speed, between different OF speeds and between the 2 VEs.
- **Position sensors:** with the use of the position sensors of the Lokomat, it is possible to measure the range of motion (°) of the 4 joints (bilateral hip and knee).

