2.8 Statistical analysis

Statistics will be performed using SPSS (IBM, Chicago, IL). The significance level will be set on 5%. Descriptive statistics will be calculated for baseline participant characteristics. Means and standard deviations will be calculated for continues variables and frequencies and percentages for categorical variables. Active participation will be measured continuously during the session. Data analysis of the average of every minute will be conducted. To investigate the effect of time, the different OF speeds, and the different VEs, repeated-measures ANOVA (within-between subject design) will be done.

3. Funding

The author disclosed receipt of the following financial support for the research, authorship and/or publication of this study: fellowship of the Vrije Universiteit Brussel for one year.

4. References

- [1] I. Schwartz and Z. Meiner, "Robotic-assisted gait training in neurological patients: who may benefit?," (in eng), *Ann Biomed Eng*, vol. 43, no. 5, pp. 1260-9, May 2015.
- [2] H. K. Kang, Y. Kim, Y. Chung, and S. Hwang, "Effects of treadmill training with optic flow on balance and gait in individuals following stroke: randomized controlled trials," *Clinical Rehabilitation*, vol. 26, no. 3, pp. 246-255, Mar 2012.
- [3] O. Stoller, M. Waser, L. Stammler, and C. Schuster, "Evaluation of robot-assisted gait training using integrated biofeedback in neurologic disorders," (in eng), *Gait Posture*, vol. 35, no. 4, pp. 595-600, Apr 2012.
- [4] E. Swinnen, D. Beckwee, D. Pinte, R. Meeusen, J. P. Baeyens, and E. Kerckhofs, "Treadmill training in multiple sclerosis: can body weight support or robot assistance provide added value? A systematic review," (in eng), *Mult Scler Int*, vol. 2012, p. 240274, 2012.
- [5] I. Schwartz *et al.*, "Robot-assisted gait training in multiple sclerosis patients: a randomized trial," (in eng), *Mult Scler*, vol. 18, no. 6, pp. 881-90, Jun 2012.
- [6] K. Y. Nam, H. J. Kim, B. S. Kwon, J. W. Park, H. J. Lee, and A. Yoo, "Robot-assisted gait training (Lokomat) improves walking function and activity in people with spinal cord injury: a systematic review," (in eng), *J Neuroeng Rehabil*, vol. 14, no. 1, p. 24, Mar 23 2017.
- [7] A. Lamontagne, J. Fung, B. J. McFadyen, and J. Faubert, "Modulation of walking speed by changing optic flow in persons with stroke," *Journal of Neuroengineering and Rehabilitation*, vol. 4, Jun 2007.

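### The single power of 0.80 fits the optic flow (OF) effect and the OF-by-environment interaction, under unstated inputs; it does not carry over to the overall comparison of the two virtual environments (VE), 14 versus 14

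*Combined protocol and SAP*

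**What the plan says.** Section 2.2.1 (Number) sizes the study with a repeated-measures ANOVA of the within-between type at f=0.25, described as moderate, and alpha 0.05: "power of 0.80 for 2 groups and 3 conditions, a total of 28 participants, divided equally in 2 groups, need to be recruited". Drop-outs are replaced until each group has 14 completers. The section gives no rho or epsilon and does not say which effect of the ANOVA the power refers to.

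The first aim in section 1.2 is the effect of OF speed, which varies within participants. Then: "The second aim is to investigate the effect of two different VEs on active participation during RAGT". Sections 2.1 and 2.5 assign one VE per participant by 1:1 randomisation, so VE is a between-group factor.

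Section 2.7.1 plans, for the torques, "to compare the amount of force in time within one OF speed, between different OF speeds and between the 2 VEs", and sets the same comparisons for EMG. Section 2.8 says: "To investigate the effect of time, the different OF speeds, and the different VEs, repeated-measures ANOVA (within-between subject design) will be done". It adds: "Data analysis of the average of every minute will be conducted". No power, detectable effect or expected difference is given for VE, and 2.8 has no rule for reading a non-significant VE result.

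**The concern.** A repeated-measures ANOVA with two groups and three conditions yields tests of very different power. Differences between conditions within a person are free of between-person variation, so a higher rho helps them. The overall VE effect compares 14 people with 14 others, and a higher rho hurts it, because repeated measures on one person then add less information. One power figure cannot describe both kinds of test unless the plan says which is meant.

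Both aims rest on the same 28 participants and only one figure is quoted, so it is easy to carry 0.80 over to the VE question. A non-significant VE result could then be taken to show that the type of environment does not matter. Section 1.1 presents this study as a step before testing neurological patients, so such a reading could shape the next study.

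**Working it through.** **Inputs from the plan:** f=0.25, alpha 0.05, N=28, k=2 groups, m=3 conditions (2.2.1). **Assumed, because not stated:** rho, shown over a range; epsilon, 1 unless noted; the same f for VE as an illustration. Power is from the noncentral F distribution.

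**Step 1. Reproduce the plan's figure.** For the OF main effect and the OF-by-VE interaction (identical when k=2):

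lambda = epsilon × f² × N × m / (1 − rho), with 2 × epsilon and 52 × epsilon df.

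At rho 0.5 and epsilon 1: lambda = 0.0625 × 28 × 3 / 0.5 = 10.5 and power is 0.812. At N=26 it is 0.778. So 28 is the smallest even N that reaches 0.80. The inputs rho 0.5 and epsilon 1 are back-calculated, not read from the plan, and they matter: power is 0.66 at rho 0.3, 0.96 at rho 0.7, and 0.72 at rho 0.5 with epsilon 0.75.

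**Step 2. Overall VE effect, three condition means, no covariate.**

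lambda = f² × N × m / (1 + (m − 1) × rho), with 1 and 26 df.

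At rho 0.5: lambda = 0.0625 × 28 × 3 / 2 = 2.625 and power is 0.345.

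| rho | OF and OF-by-VE power | VE power | f for 80% VE power |
|---|---|---|---|
| 0.3 | 0.66 | 0.41 | 0.40 |
| 0.5 | 0.81 | 0.35 | 0.45 |
| 0.7 | 0.96 | 0.30 | 0.49 |

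At rho 0, VE power is 0.60, its maximum for rho of 0 or more.

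**Step 3. Minute averages.** Section 2.8 analyses minute averages, 3 × 7 = 21 per person. If f and rho are taken to refer to those (m=21), VE power is 0.60 at rho 0.3, 0.42 at 0.5 and 0.33 at 0.7. It reaches 0.80 only at rho of about 0.17 or lower. The documents give no value for this correlation.

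**Step 4. Precision.** With two equal groups, f=0.25 is a difference of 2 × 0.25 = 0.50 single-condition SD. The three-condition mean has SD sqrt((1 + 2 × rho)/3), which is 0.816 single-condition SD at rho 0.5. The same difference is therefore 0.50/0.816 = 0.61 SD of that mean. The 95% CI half-width without a covariate is t(26 df) × sqrt(((1 + 2 × rho)/3) × (2/14)). This gives 0.57, 0.63 and 0.70 single-condition SD at rho 0.3, 0.5 and 0.7. Each exceeds 0.50, so even an observed difference of zero would leave the planning effect inside the interval. Without a covariate, the half-width falls below 0.50 only at rho under about 0.12.

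**Step 5. What a baseline covariate could add.** Suppose the baseline minute correlates with each condition as the conditions do with each other. Its correlation with the outcome mean is then r = rho / sqrt((1 + 2 × rho)/3), or 0.41, 0.61 and 0.78 at rho 0.3, 0.5 and 0.7. Simulated ANCOVA power at f=0.25 (20,000 trials each, chance baseline imbalance included) is about 0.47, 0.49 and 0.61. The formula lambda/(1 − r²) with 25 df gives slightly more: 0.48, 0.50 and 0.63. If r is only 0.3 at rho 0.5, the formula gives lambda = 2.625/0.91 = 2.88 and power of about 0.37, little better than 0.35.

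**The case against.** The strongest reply is that 2.2.1 contains no mistake. It names its test family, effect size, alpha, groups and conditions, and 28 follows from rho 0.5 and epsilon 1. It nowhere claims to power both aims, and sizing a study on one effect while treating another as secondary is ordinary practice. All of this stands. A reader might infer that N=28 is miscalculated, or that the plan promises 0.80 for VE; the documents support neither.

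Second, neither section 1.2 nor 2.8 speaks of an overall or main effect of VE. Part of the VE question is whether the OF response differs by environment, and that interaction is covered at 0.81. This stands in part. But section 1.2 states the VE aim without reference to OF speed, and 2.8 lists VE as an effect alongside OF speed, so the overall comparison is the natural reading. If only the interaction was meant, 2.2.1 can say so.

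Third, 0.35 rests on an assumed rho and on an f never tied to these two environments. That is right: it is an illustration, not the trial's power. A true VE effect of f about 0.45 would have 80% power at rho 0.5.

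Fourth, a covariate is a design improvement, not a correction to 2.2.1, and its gain may be small. That also stands, so it is offered as separable.

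**Conclusion.** The concern holds as a question of what the 0.80 covers. It reproduces for the OF main effect and the OF-by-VE interaction, conditional on a rho and epsilon that the plan does not state. It does not carry over to the overall VE comparison. With f=0.25, three condition means and no covariate, VE power stays at or below 0.60 for every rho of 0 or more and is about 0.35 at rho 0.5. Under the minute-average reading it could reach 0.80, but only at rho of about 0.17 or lower.

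A reader might go further and conclude that the trial is too small or that the VE aim must be dropped. The documents do not support that, because they set no VE effect that the trial must detect and no power target specific to VE. The arithmetic is firm; the size of the shortfall depends on the assumed f and rho. It should be fixed, at the level of what is stated, how VE is reported and, optionally, how it is tested.

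**What to change.** 1. **Section 2.2.1.** State the rho and epsilon used. Say that 0.80 applies to the OF main effect and the OF-by-VE interaction under those inputs, and not to the overall VE effect. Give the detectable VE effect at N=28 for the VE test that 2.8 will use. Without a covariate, 80% power needs f of about 0.45 at rho 0.5 (0.40 at rho 0.3, 0.49 at rho 0.7).

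2. **Section 2.8.** Report the VE effect as a between-group difference with its 95% CI, and do not read a non-significant result as absence of effect. State which SD is used if the difference is standardised. For scale, the half-width at rho 0.5 without a covariate is about 0.63 single-condition SD, against a planning difference of 0.50 on the same scale.

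3. **Optional improvement.** Section 2.4 says "participants will be habituated to walking in the Lokomat without the virtual reality", and then: "When the Lokomat settings are defined, the Lokomat will be stopped for a moment so that the virtual reality can be added". For each outcome, keep the last full minute of that walk at the final settings. It precedes any exposure to the assigned VE. Use it as the covariate in an ANCOVA of each participant's mean over the three OF conditions, as the planned VE test for that outcome. Leave the OF and OF-by-VE tests unchanged.

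**Cost.** Parts 1 and 2 cost a few sentences and a less favourable stated figure, and they stand without part 3. Part 3 costs 1 df in the VE test and at most one extra minute in a 45-minute session. Electrodes are already in place, and 2.8 says "Active participation will be measured continuously during the session", so it may need no new recording; 2.4 does not say explicitly that data are kept during the walk without VR, so this should be confirmed. The gain depends on a correlation that the documents do not give. No extra participants are needed.

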2.5 Randomization

Subjects who agree to participate in this study will be equally randomized in a 1:1 ratio into 2 groups. For randomization, sealed envelopes will be prepared in advance and marked on the inside with a VE + or VE -. During the intervention, the speed of the OF (slow, matched or fast) will also be randomized. To participants, it will only be said that they will have to walk in the Lokomat with the VR for 21 minutes. They will not know that and when the OF speed will change.

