2.6 Materials

Surface EMG electrodes will be used to measure the muscle activity of the Mm. rectus femoris and Mm. biceps femoris. Surface EMG data will be captured with the ME6000 EMG-system (Mega Electronics Ltd) using Conmed Cleartrace electrodes (Ag/AgCl) with an active diameter of 10mm.

The Lokomat has a biofeedback system that measures and displays participants' activity in real-time. With the use of force sensors, this biofeedback system measures the force of the Lokomat's drive motors. If the participant actively moves with the programmed gait pattern, the power required from the drives is small. The less active the participant is, the greater the drive force required to move his limbs according to the preprogrammed pattern. With this approach, two values are calculated for each driven joint; one for the swing phase, the other for the stance phase. This provides 8 biofeedback values per step cycle to characterize the degree of activity of the patient. Besides force sensors, the Lokomat also comprises position sensors. These sensors will be used to measure the range of motion (ROM) of the hip- and knee joints.

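### Replacing dropouts and analysing only by repeated-measures ANOVA leaves the VE comparison among completers; the bias is probably small and cheap to reduce

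*Combined protocol and SAP*

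**What the plan says.** Section 2.2.1 sets the recruitment target by completion: "In case subjects drop out, additional participants will be tested till 14 participants in each group completed all conditions".

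Section 2.8 gives the inferential analysis in one sentence: "To investigate the effect of time, the different OF speeds, and the different VEs, repeated-measures ANOVA (within-between subject design) will be done". It works on minute averages ("Data analysis of the average of every minute will be conducted") and says that recording is continuous. Section 2.4 has three OF speeds "that will be presented in a random order for 7 minutes each". Section 2.7.1 uses the per-minute EMG values "to compare the amount of muscle activity in time within one OF speed, between different OF speeds and between the 2 VEs".

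On allocation, section 2.5 says "Subjects who agree to participate in this study will be equally randomized in a 1:1 ratio into 2 groups", using sealed envelopes prepared beforehand. Section 1.2 makes the VE comparison the second aim.

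The document defines no analysis set, no rule for partial data, no sensitivity analysis and no reporting of dropouts by group.

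**The concern.** A participant who stops after the first OF block leaves seven recorded minutes. The standard repeated-measures ANOVA drops anyone with an empty within-subject cell, so under the plan as written those minutes contribute nothing and another person takes the place.

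Replacement restores the count of 14 per group. It does not restore the randomised comparison, because people who leave one VE are replaced by people who tolerate it. VE is the only between-group factor, so the second aim depends on the two groups staying comparable. The OF aim is a within-person contrast and is less exposed, although it too would describe completers only.

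**Working it through.** **1. The plan's own figure.** Section 2.2.1 gives f = 0.25, alpha 0.05, power 0.80, 2 groups and 3 conditions. The correlation and sphericity settings are not stated; I assume 0.5 and 1. For the within-between interaction, the noncentrality is f²·N·m/(1 − ρ) = 0.0625 × 28 × 3 / 0.5 = 10.5 on 2 and 52 df, which gives power 0.812. So 28 reproduces. With 26, 24 or 22 completers, power would be 0.778, 0.740 or 0.697. Replacement therefore protects planned power.

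**2. Completer bias in closed form.** Inputs, all assumed: dropout rate p in each VE, and correlation r between outcome and the tendency to stop. With a latent normal tendency, the completers' mean shifts by r·φ(z_p)/(1 − p):
- p = 0.05: 0.103/0.95 = 0.109r
- p = 0.10: 0.175/0.90 = 0.195r
- p = 0.20: 0.280/0.80 = 0.350r

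The bias in the VE difference is the difference between the two groups' shifts. It is zero if r = 0 in both, or if rate and r are the same in both. At r = 0.5, 10% v 5% gives 0.5 × (0.195 − 0.109) = 0.043 SD, and 20% v 5% gives 0.5 × (0.350 − 0.109) = 0.121 SD (0.072 at r 0.3, 0.169 at r 0.7). Equal rates alone are not a guarantee: 10% v 10% with r = 0.5 in one VE and 0 in the other gives 0.5 × 0.195 = 0.097 SD.

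These are in SDs of the quantity that drives stopping. If that is the first block, and blocks correlate 0.5 (assumed), the mean of the three blocks moves by (1 + 0.5 + 0.5)/3 = 0.667 of it: about 0.03 block SD at 10% v 5%, and about 0.05, 0.08 and 0.11 at 20% v 5%.

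**3. Simulation at trial size.** 10,000 trials per row; three block means in random OF order; stopping after block 1; no true VE effect. Replacements take the next envelope until both groups have 14 completers. The completer test uses the first 14 per group. The mixed model uses all recorded blocks, with REML and Satterthwaite df. Bias is in block SD, with Monte Carlo SE 0.003.

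| Assumed dropout, and what stopping depends on | Completer bias (type I error) | Mixed-model bias (type I error) |
|---|---|---|
| 10% v 5%, block 1, r 0.5 | 0.023 (4.9%) | −0.004 (4.9%) |
| 20% v 5%, block 1, r 0.3 | 0.041 (4.9%) | −0.003 (5.0%) |
| 20% v 5%, block 1, r 0.5 | 0.075 (5.7%) | −0.001 (5.0%) |
| 20% v 5%, block 1, r 0.7 | 0.108 (6.3%) | 0.003 (4.9%) |
| 10% v 10%, block 1, r 0.5 v 0 | 0.059 (5.4%) | −0.004 (4.9%) |
| 20% v 5%, unrecorded blocks 2 and 3, r 0.5 | 0.088 (6.1%) | 0.036 (5.2%) |

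In the last row 0.036/0.088, about 40% of the bias, remains.

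For scale, a person mean has variance 0.5 + 0.5/3 = 0.667, so the VE standard error is √(0.667 × 2/14) = 0.31 block SD. A bias of 0.075 is about a quarter of that.

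A harsher model confines dropout to one VE, with odds rising by a factor e per SD of lower activity. It gives completer bias of 0.04, 0.08, 0.14 and 0.18 SD at baseline rates of 5, 10, 20 and 30%, and about zero when all recorded data are used.

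**4. Which mixed model.** The rates of about 5% above come from block means. They do not carry over to a minute-level model with only participant and participant-by-OF intercepts, which treats minutes within a block as exchangeable. In two simulations of complete data (28 people, 3 × 7 minutes, no true effects, SDs assumed), that model's type I error for the time effect was about 6 to 10% under within-block AR(1) correlation, and about 9 to 21% with person-specific time trends. A Greenhouse-Geisser ANOVA on the same data held about 4 to 6%. The time effect therefore needs its own treatment.

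**The case against.** The strongest reply is that this is a single session with 21 minutes of walking in healthy adults, and section 2.2.2 excludes vestibular and visual deficiency. No document supports 20% dropout, a fourfold imbalance between VEs, or any link between stopping and outcome. At 10% v 5% the type I error does not move. Replacing dropouts matches the basis of the sample size. All of this stands, and it is why the point is low in severity.

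It is also fair that the precision gain from the mixed model is overstated if taken at face value. At 20% v 5%, RMSE falls from 0.31 to 0.285, but the next-envelope rule yields 14.0 v 16.3 completers. A completer analysis of all of them would already have a standard error of √(0.667 × (1/14.0 + 1/16.3)) = 0.298. Nearly half the gain comes from testing more people.

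Three stronger readings are tempting, and the documents do not support them:
- That the plan discards partial data. It never says so; this is a consequence of the only method named.
- That one lost minute excludes a participant. Minute averages with time as a factor suggest 3 × 7 = 21 cells, but the layout is not stated, section 2.2.1 sizes the test on 3 conditions, and a brief artefact need not remove a minute average. With 1% of minutes unusable (assumed), about 26 to 28 of 28 are kept if losses cluster. The figure 28 × 0.99²¹ = 22.7 needs independent losses, the least plausible case.
- That replacements fall outside randomisation. Section 2.5 randomises everyone who agrees to take part, which arguably covers them. Only the spare envelopes and the point at which recruitment ends are not spelled out.

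**Conclusion.** The point holds as a low-severity one. A completion-based target combined with an ANOVA that needs every within-subject cell would leave dropouts' recorded blocks unused and make the second aim a comparison of completers.

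A reader might infer that the VE result will be biased. That does not follow. Bias requires that stopping is related to outcome and differs between VEs in rate or in that relation. If both hold, its size is about 0.02 block SD with no type I inflation at 10% v 5% (r 0.5), and about 0.04 to 0.11 block SD at 20% v 5% (r 0.3 to 0.7). Every rate and correlation here is assumed, because the documents give none. If nobody drops out, the bias is zero. Planned power is not in question.

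The case for acting is that the change is cheap, and that a method fixed in advance is more credible than one chosen after seeing who stopped.

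**What to change.** **Section 2.8.** Estimate the OF, VE and OF-by-VE effects with a linear mixed model on OF-block means, each the average of the minutes recorded in that block. Include every randomised participant with at least one recorded block, in the assigned VE group, with a participant random effect and Satterthwaite or Kenward-Roger degrees of freedom. Keep the completer ANOVA as a sensitivity analysis. Report dropouts by VE group and OF block.

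For the time effect, either keep the repeated-measures ANOVA with Greenhouse-Geisser correction (still an analysis of completers), or use a minute-level model that also has person-specific time effects and serial correlation within block. Do not use participant and participant-by-OF intercepts alone.

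**Sections 2.2.1 and 2.5.** State that each replacement takes the next concealed envelope, what ends recruitment, and that every randomised participant with data stays in the analysis.

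**Cost.** A little more analysis work and some spare envelopes. With spares in blocks of 4 and at least 14 completers required per group, the expected number tested is 31.3 rather than 30.3 at 10% v 5% dropout, and 34.7 rather than 32.2 at 20% v 5%: one to three more people. Ending at 28 completers in total needs 30.3 and 32.0. The groups may then be slightly unequal, but a 12/16 split raises the VE standard error by only 1%.

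**What it does not solve.** The model cannot help with people who stop before any recording, and helps only in part if stopping depends on unrecorded blocks. For EMG it also needs the MVIC normalisation to be available for dropouts. Section 2.4 describes that test after the walking conditions without stating its timing, and the example session schedule does not show it, so its timing should be stated too.
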